## 5.5 Study Evaluations

### 5.5.a Phone screening.

The phone script (Appendix L) outlines the phone screening conversation with potential participants. During the phone call to ascertain interest in participating in the study, study staff will also ask potential participants specific questions regarding all of the inclusion and exclusion criteria including: access to a phone, ability to stand without assistance, ability to take shoes and socks on and off, ability to read, MOVE! participation in last 4 months, blindness, pregnant or planning pregnancy in next 12 months, current height and current weight, insulin use, Veteran status, cognitive impairment, questions about their phone, access to the internet, smart phone, cell service provider and any weight loss medication/supplements or nutritional product use. If they “screen out” they will be thanked for their time and enrollment will not proceed, though they will be offered participation in the associated repository 00982 if interested. If the potential study participant is eligible, a study team member will set up a convenient time to meet them for an in-person appointment. We will also be collecting patient self-reported demographic data including gender, ethnicity and race, and questions about owning a smartphone or a phone that can receive text messages, and cell phone service provider. Demographic data and cell phone/service provider questions will not be used to determine eligibility.

At the in person (baseline) appointment after the participant has completed the HIPAA authorization and consent form (described in section 5.3), participants will be given access to the baseline survey in the portal (Appendix C). The participant will be given all the study information, resources and will be weighed.

**5.5.b. Surveys.** The survey will be given at the four intervals: baseline, 16 and 32 weeks and one year. The survey will be completed through the patient portal. The survey will only be active for three weeks following their 16 week, 32 week, and one year appointments. The baseline survey will be active from the day of their baseline visit until two days before their first weigh-in is due (6-12 days, depending on their chosen weigh day). Coordinators can edit the active survey dates if the participant is unable to complete the survey before its due. However, if the participant is unable to complete the baseline survey within 4 weeks they will be withdrawn (see Passive Withdraw, section 5.7.b). The survey is a comprehensive assessment of standardized survey instruments used in clinical trials and clinical operations. The assessment has a combination of assessments to create a wide-ranging survey tool covering items from race, food insecurity, eating habits to lifestyle and previously use theories for weight loss.

#### Summary of survey components:

Screening for motivation to lose weight, and free text field on what motivations are.

#### Demographics):

VA MOVE11 partial survey: The survey is the standard enrollment intake survey of the MOVE! program. It covers, height, weight, BMI, ethnicity, race and various health behavior and lifestyle indicators, Regulation of eating behavior survey (REBS): Questions to determine the internal motivation or regulation of a behavior.

Health status from the SF12

Additional sleep and alcohol questions

Financial distress questions from the Prawitz Financial Distress Scale

Three factor eating questionnaire (TFEQ-18): Questions regarding eating patterns and behaviors.

Personal Health Questionnaire Depression Scale (PHQ-8): This is an established diagnostic and severity measure for depressive disorder in large scale clinical trials.

International physical activity questionnaire (IPAQ): Activity level over 7 days, from vigorous, moderate, walking and sitting.

Weight Efficacy Lifestyle Questionnaire Short Form (WEL-SF): Confidence level in controlling certain behaviors

Food insecurity questionnaire (from NHIS): Eating behaviors and food purchasing behaviors based on financial stability and socio-economic status.

NHANES Weight Loss Strategies: Covers a variety of common methods used for weight loss and participants use of them.

Additional Questions: These questions ask a participant why they want to lose weight and how motivated they are to lose weight.

Participants will complete the survey at all four points in the study through the online patient portal (baseline, 16 weeks, 32 weeks, one year). Participants will complete the surveys in the participant portal. The information from the survey will then be downloaded from the secure Austin server and saved directly into the J:drive access database.

**5.5.c. Weight measurements.** Participant weights will be taken at the in-person visits. The participant will be asked to step onto a scale. The weight shown on the scale will be recorded. After the participant, has completed the survey instrument and had their weight taken, they will be randomized to one of three groups, as described in section 5.4. Weight measurements will be taken at all four in-person visits. Participants will also be counseled to weigh themselves daily before eating and after using the bathroom and recording their weight weekly into the portal.

#### **5.5.d. Study interview (Appendix G).**

We will conduct post-intervention, semi-structured phone interviews with selected Veterans from each arm (10-30 participants from each arm, or until saturation). Participants selected for an interview will receive a letter in the mail followed by a recruitment phone call to schedule (letter submitted with modification). The goals of the qualitative interviews are: 1) to provide depth to the quantitative analyses of patient surveys and 2) learn what worked and did not work in the present trial in order to run a better trial in the future. Participants who are still enrolled in the study at week 32 will be interviewed after the primary outcome measurement at the 32 week weigh-in. On occasion it is not convenient for some participants to be interviewed between week 32-52 of the study. Participants will be sent a letter for the interview and the two follow-up efforts between week 32-52, but to better accommodate participants with busy schedules we will interview participants after their week 52 visit if they wish to participate and if that is most convenient for them. Groups will be purposively sampled to include both male and female Veterans. We will use a semi-structured interview guide (Appendix G) with open-ended and semi-structured follow-up questions. Structured open-ended prompts will be used in order to elicit rich descriptions of patients' experiences with specific aspects of the intervention, including how the discontinuation of the reward affected their behaviors, resources they used and motivations. Interview questions will elicit information about what aspects of the non-financial rewards (evaluability, justifiability, separability/instrumentality, and social reinforcement) were motivating; how the reward affected behaviors; whether experience-based rewards such as tickets to an event had a lingering and positive effect on motivation; and whether other features could be added to create a more acceptable reward program. We will also interview usual care patients to elicit descriptions of experiences associated with other Veterans receiving rewards when they did not. Interviews will be conducted via telephone and recorded on a secure VA digital recorder then immediately moved to a secure VA data server. Interviewers will take notes for each interview including descriptive data (time, date, etc.), theoretical memos, methodological issues, and reflexive memos (personal responses). We expect the interviews to take 30-45 minutes. All interviews will be recorded using either Microsoft Skype for Business, VA-issued recorder, or the Audacity software program and will be saved directly or immediately transferred onto the secure VA network, in an access-restricted folder behind the VA firewall. ATLAS.ti software will be used to code the interview findings. Consent to participate in this interview is covered under the study Consent Form that is signed at baseline; however, interviewers will

also obtain verbal approval to record the interviews immediately prior to conducting them. Regardless of the participant's enrollment in the repository their interview and any qualitative data will not be included in the repository.

As soon as we have any initial findings or when the last participant is done with the study we will mail all study participants preliminary study findings.

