### 3.0 Objectives

The proposed study is based on the hypothesis that the regain found in prior reward studies was due in part to their use of financial rewards, and financial rewards may make patients especially susceptible to regain. Experiments in behavioral economics have found that when participants were provided financial rewards for performing a task, their behavior toward the task was defined by reciprocity—the effort the participants gave was proportional to the amount of money that they were given. When participants were given non-financial rewards, they exhibited no reciprocity—the effort was consistently high and did not vary with the quantity of the non-financial reward. These findings have been confirmed in field studies, and experiments using functional MRIs: money as a reward makes us think and behave differently. By using financial rewards, prior trials may have invoked money-market norms of reciprocity, such that patients' efforts toward weight loss were high when rewards were offered, and reduced when they were discontinued. We hypothesize that non-financial rewards, such as tickets to a Seattle Mariners baseball game, will not invoke reciprocity or the consequent weight regain. We also hypothesize that the affective or emotional characteristics of non-financial rewards can make them more powerful than financial rewards. A patient's thoughts about receiving a non-financial reward, such as tickets to baseball game, can create a positive emotional reaction that can be more salient than the cash value of the reward.

The goal of this study is to test, through a randomized trial, the effectiveness of providing obese Veterans with financial or non-financial rewards for losing 1 lb. per week over 16 weeks. The primary outcome is weight loss at 32 weeks—16 weeks after the discontinuation of the rewards. Secondary outcomes include weight loss at 16 weeks and 12 months. The specific aims are outlined below.

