## 5.0 Study Procedures

### 5.1 Study Design

This is a randomized controlled trial that will enroll participants on a rolling basis. Each participant will be enrolled for approximately 1 year. However, participants may also choose to be consented into the associated repository, "Rewards Project Data Repository (MIRB-00982)." Please refer to the attached study flow chart for a visual depiction of study events and timeframe of participant activities. An overview of what the website (portal) looks like and functionality is in the document titled "website mock up," and portal screen shots.

There are two points of randomization. After patients are enrolled in the study, they will be enrolled in the portal. At portal enrollment, they will be randomized to either receive a wireless (Blipcare) or the wireless Blipcare scale and the Connect device. At enrollment all participants will receive the Blipcare wireless scale. There are two different types of scales: wireless Blipcare scales and a non-wireless digital battery powered Taylor scales. The Blipcare scales are wireless scales that transmit weight data through a cellular hub, "Connect." Regardless of the scale the participant receives, all participants will be encouraged to record their weight manually to better keep track of their weight (Appendix N). All participants in all arms will also record their weight into the study portal as outlined below. The participants that receive a Blipcare scale with the Connect device will have their weight recordings sent automatically to research study staff via the Connect device. At the 16-week study visit, participants may be asked to exchange their scales for a Taylor scale, depending on our Blipcare scale inventory. Due to the mechanism of reusing the Blipcare scales and Connects, some participants may only receive Taylor scales, and some participants may be able to keep their Blipcare scales.

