Numerous participants have requested to learn the results of the study. We are planning to send basic study results in three separate newsletter mailings, spring 2021, fall 2021 and spring 2022. All newsletters and letters will be approved by the IRB prior to mailing.

After all manuscripts are published (estimated December 2022), all human subject identifiable files and crosswalks (if applicable) will be destroyed in accordance with approved data destruction policies. Electronic media used to store identifiable data will be cleaned or destroyed in compliance with governing information security regulations. Should there be improper disclosure the facility ISO and Privacy Officer will be notified within one hour of becoming aware of the situation.

While we will make every effort to keep information confidential, no system for protecting confidentiality can be completely secure in this operational context. Individuals may choose to share with others the fact of their participation or opinions about the rewards, the survey, the interview or any other part of the study. We will not disclose participation in the study or responses to any questions to anyone outside our research team.

Interviews will be recorded using Microsoft Skype for Business, a VA-issued recorder, or the Audacity software program and will be saved directly or immediately transferred onto the secure VA network, in an access-restricted folder behind the VA firewall. ATLAS.ti software will be used to code the interview findings.

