### **5.1.c. Study population.**

We will approach approximately 5,000 patients with introductory letters. We will enroll and consent up to 350 patients. Our target enrollment is 280 Veterans total—80 in the no-reward arm, and 100 in each of the two reward arms. As of 3/6/2020 we have currently stopped enrolling. We have presently enrolled 274 participants. Once we have additional information about coronavirus to make an informed decision about recruitment we will either formal close enrollment at 274 or we will continue.

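### Section 5.5.d lets preliminary findings go to all participants before follow-up ends, section 5.1.b gives a different timetable, and neither restricts by-arm content or waits for completed outcomes

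*Combined protocol and SAP*

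**What the plan says.** The last sentence of section 5.5.d (Study interview) sets a release rule, "we will mail all study participants preliminary study findings", and gives it two alternative triggers: "As soon as we have any initial findings or when the last participant is done with the study". The recipients are all participants, not only those who have finished.

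Section 5.1.b (Potential risks) gives a different timetable: "We are planning to send basic study results in three separate newsletter mailings, spring 2021, fall 2021 and spring 2022". Its only control is that "All newsletters and letters will be approved by the IRB prior to mailing". It does not say that it replaces the rule in section 5.5.d.

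The setting for both statements is as follows:

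- Section 5.1: "This is a randomized controlled trial that will enroll participants on a rolling basis" and "Each participant will be enrolled for approximately 1 year".
- Section 3.0: "The primary outcome is weight loss at 32 weeks—16 weeks after the discontinuation of the rewards". Weight loss at 16 weeks and at 12 months is secondary. Hypothesis 1c concerns regain from week 16 to week 32 and to 12 months.
- Section 5.1.a: participants learn their arm after the baseline survey. From 3/6/2020 follow-up visits are held by phone, and section 5.1.b treats the weights given there as self-reported.
- Section 5.1.c: enrolment stood at 274 when it stopped on 3/6/2020, and once more is known about coronavirus "we will either formal close enrollment at 274 or we will continue".

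**The concern.** Because the two triggers in section 5.5.d are joined as alternatives, the first can be met while many participants are still being followed. With rolling entry, 16-week results (the data for hypothesis 1b) can exist well before later entrants reach week 32 or month 12.

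The trial is open to participants and the outcome depends on their effort. A person who hears that their reward type works, or that their arm tends to regain, may try harder, give up, shade a self-reported weight, or stop attending. If those reactions differ by arm, the later between-arm comparisons measure the mailing as well as the rewards. The comparison most exposed is hypothesis 1c, whose window (week 16 to week 32 and to 12 months) is when an early mailing would arrive. The primary outcome would be touched only by a mailing that reaches people before week 32.

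The protocol guards this boundary elsewhere: section 5.5.d schedules interviews of people still enrolled at week 32 after the 32-week weigh-in. The mailing has no comparable rule.

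**Working it through.** The plan states no figure on this point, so there is none to reproduce. The check compares the two release rules with the calendar of outcomes.

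**1. Calendar if enrolment stays closed at 274**

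Inputs: latest possible baseline visit 6 March 2020 (section 5.1.c); outcomes at 32 weeks (224 days) and 1 year (365 days); a lag from baseline visit to study start of 0 to 28 days, the upper end being the four weeks allowed for the baseline survey that precedes randomization (sections 5.5.b and 5.7.b); a 21-day survey window (section 5.1.a).

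| Event for the last person enrolled | Lag 0 days | Lag 28 days |
|---|---|---|
| 32-week weight (+224 days) | 16 Oct 2020 | 13 Nov 2020 |
| 12-month weight (+365 days) | 6 Mar 2021 | 3 Apr 2021 |
| 12-month survey window closes (+21 days) | 27 Mar 2021 | 24 Apr 2021 |

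A spring 2021 newsletter therefore follows every scheduled 32-week weight. It can precede a 12-month weight only if it goes out before about 6 March to 3 April 2021.

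**2. Calendar if enrolment resumes**

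A participant receives the newsletter before the 32-week weight if enrolled later than the mailing date minus 224 days.

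- Mailing on 1 March 2021: enrolled after 20 July 2020.
- Mailing on 31 May 2021: enrolled after 19 October 2020.

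Reaching the target of 280 would add 280 − 274 = 6 people. Section 5.1.c allows consent of up to 350 but states no plan to exceed 280.

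**3. Exposure under the first trigger of section 5.5.d (illustration)**

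Assumption: 274 people enrol uniformly over 15 months (the planning period in section 5.2.b), that is 15 × 30.44 = 456.6 days. The actual accrual pattern is not given. If findings are mailed when the last enrolled person reaches day *a*, the number who have not reached day *b* is 274 × (*b* − *a*) / 456.6.

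- All 16-week data in (*a* = 112), no 32-week weight (*b* = 224): 274 × 112 / 456.6 ≈ 67 (25%).
- All 16-week data in, no 12-month weight (*b* = 365): 274 × 253 / 456.6 ≈ 152 (55%).
- All 32-week data in (*a* = 224), no 12-month weight: 274 × 141 / 456.6 ≈ 85 (31%).

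An earlier mailing would reach more people before their outcomes. These are counts of people exposed, not estimates of bias.

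**4. The two release rules side by side**

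| | Section 5.5.d | Section 5.1.b |
|---|---|---|
| When | Any initial findings, or last participant finished | Spring 2021, fall 2021, spring 2022 |
| Content | Preliminary findings | Basic results |
| Limit on by-arm content | None | None |
| Tied to completed outcomes | Only through the second trigger | No |
| Other control | None stated | IRB approval |

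**The case against.** The strongest reply is that the harm needs several steps the documents do not plan. Section 5.6.a schedules no interim comparison of arms. The futility assessment in section 6.2 is linked to data loss from recruitment, retention or data collection. Someone would have to run an early between-arm analysis, decide to mail it, and obtain IRB approval for the letter. The sentence in section 5.5.d also comes directly after text on interview data, so it may mean qualitative findings. The only dated plan, in section 5.1.b, starts when follow-up is nearly over.

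Much of this stands. A reader might infer that the trial intends to send weight results by arm during follow-up. The documents do not say so: by-arm content is not excluded, but neither is it stated. A reader might also infer that the primary outcome is compromised. Under the newsletter timetable with enrolment closed, it is not. Nor is it sound to count everyone still in follow-up on 3/6/2020 as exposed, since no mailing is scheduled for that date and the accrual rate is not reported. Resumed enrolment could extend follow-up past the first newsletter, but both the decision and its date were open, and the target was only 6 people away.

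The reply does not remove the point. Section 5.1.b does not withdraw the rule in section 5.5.d, and IRB approval governs neither the timing of release relative to outcomes nor by-arm content. Interview findings are not harmless either: the interviews ask how the end of the rewards affected behaviour, which bears directly on hypothesis 1c.

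**Conclusion.** The point holds in a limited, conditional form. Read literally, section 5.5.d permits findings to reach participants who know their arm before their 32-week or 12-month weight is taken. Section 5.1.b gives a different timetable without resolving the difference.

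The consequence depends on which rule is followed. Under the spring 2021 timetable with enrolment closed at 274, the exposure is marginal and confined to the last 12-month weights. Under the first trigger of section 5.5.d it could be substantial, and it reaches the primary outcome only with an early mailing or resumed enrolment. The illustrative counts rest on uniform 15-month accrual and visits held on schedule.

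The documents give no basis for the size or direction of any bias, and they do not show that an early mailing took place. This is a desirable wording correction, not a flaw in the main analysis.

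**What to change.** 1. In section 5.5.d, delete the first trigger, so that mailing waits until the last participant has finished.
2. Add a rule such as: no between-arm outcome findings, quantitative or qualitative, will be sent to participants until the last enrolled participant's 12-month weight has been recorded and the 12-month survey window has closed.
3. In section 5.1.b, tie the first newsletter to that event instead of to a season, so that the two sections agree and the rule still works if enrolment resumes.

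The cost is one deleted phrase and one added sentence. Participants may receive results somewhat later. With enrolment closed at 274, the event in step 2 falls between about 27 March and 24 April 2021, so a spring 2021 newsletter would remain possible.

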### 5.6.a. Data Analysis

All data will be analyzed at VA Puget Sound Health Care System by one of the data analysts and/or investigators.

We will use an intent to treat analysis. To test each hypothesis we will estimate an equation of the form

$\Delta Y_{it} = \beta_0 + \beta_1 Weight_{i0} + \beta_2 M_i + \beta_3 F_i + u_i$  (1) where  $\Delta Y_i$  is change in weight from baseline to follow-up time t

for patient i;  $Weight_{i0}$  is baseline weight for patient i; F is the financial rewards (arm 2); M is an indicator for assignment to non-financial rewards (arm 3); and u is a random error. To gain a small amount of efficiency we can also estimate (1) using repeated measures of change in weight from baseline to the three follow-up measures (16 weeks, 32 weeks and 12 months) using GEE models of the same form as equation (1), except with dummy variables for follow-up periods and interactions between these variables and the treatment group dummies.

Hypothesis 1a implies a test of superiority and will be assessed using two-sided tests of  $\beta_2 = 0$  for non-financial rewards, and  $\beta_3 = 0$  for financial rewards. Large positive or negative values of  $\beta_2$  and  $\beta_3$  are evidence against the null hypothesis of no difference between reward and non-reward groups.

Hypothesis 1b implies a non-inferiority test. We will reject the hypothesis that non-financial rewards are inferior to financial rewards if  $\beta_2$  is statistically significantly greater than zero (i.e., there was statistically significantly more weight loss in the non-financial reward arm than in usual care) and if  $(\beta_3 - \beta_2) < 2.5 kg$ , where  $(\beta_3 - \beta_2)$  is the adjusted difference in mean weight loss between the financial and non-financial reward arms, and 2.5 kg is half the 5 kg weight loss assumed to be clinically significant. Although there are no defined rules for choosing a range of indifference for a non-inferiority test, researchers often use half the minimum clinically significant amount. Values of  $(\beta_3 - \beta_2)$  that are statistically significantly larger than 2.5 kg are evidence against the hypothesis that non-financial rewards are not inferior to financial rewards.

Hypothesis 1c implies a test of superiority and will be assessed using two-sided tests of  $(\beta_3 = \beta_2)$  in comparisons of weight change from week 16 to week 32 and 12 months, respectively. We will use weight change at week 16 in place of weight at baseline in equation 1, such that differences in weight regain between treatment arms will be adjusted for weight lost over weeks 1-16.

Because all secondary outcomes are continuous variables, a similar equation will be used to assess changes in secondary outcomes. These analyses explore how rewards affect constructs that are believed to mediate the effect of rewards on weight loss.

Missing weight measures will be imputed using data from patients' medical records for routine medical visits and methods developed and tested via simulation by [name] et al. These methods involve estimating longitudinal mixed-effects linear models of weight collected both through the trial and at routine clinic visits as a function of polynomials of time since enrollment, with random components for patient intercept and time, and using the predicted values from this model for any post intervention day as an estimate of what the patient's weight would have been on that day if he/she kept their follow-up appointment.

We assumed a standard deviation of 11.0 lbs. for weight loss based on the results of the JAMA (2008) and JGIM (2011) trials that were conducted in the VA and demonstrated statistically significant differences in

weight loss at the end of the reward period. We used a two-sided alpha of 0.025 to account for the multiple comparisons between treatment groups (including for hypotheses 1b and 1c, which compare only two groups). We chose a clinically meaningful minimal detectable difference of 11 lbs. (5 kg). This was the weight loss experienced by the lifestyle management arm of the Diabetes Prevention Program randomized trial, which experienced lower rates of the incidence of diabetes. According to data from the 2012 NHANES, 11 lbs. is 5% of the average weight of 233 lbs. for obese men, and the FDA defines a weight loss drug as clinically effective if mean weight loss in the drug group is at least 5% of baseline weight. With these assumptions we would require full data on 21 patients per treatment arm at follow-up, or 28 assuming 20% loss to follow-up, in order to have 80% power to reject hypothesis 1a. In order to conduct subgroup analyses with reasonable precision, and to increase the power to detect differences in weight regain between reward groups (hypothesis 1c), we will increase enrollment to 80 patients in the no-reward arm, and we will increase the ratio of patients randomized to control versus either reward group from 1:1 to 1:1.25 for a total of 280 patients (80 usual care+100 in each reward arm). This provides a minimum detectable difference of 5.1 lbs. between treatment arms, and 4.5 lbs. if the reward arms are combined. In the three studies in Table 1, the average weight loss in the control groups at the end of follow-up was 1.6 lbs. Thus, we expect 80% power to detect weight loss as small as 6.7 lbs. in each reward group. At the end of the reward period, the average weight losses in the reward groups was 10 lbs. (range, 14 to 3.7) among the trials in Table 1. In the JAMA (2008) study, 50% of the reward group achieved their goal of 16 lbs. weight loss in 16 weeks. Thus, we have the power to detect achievable and clinically important weight losses across treatment arms.

With 100 patients per reward arm, the minimum detectable difference for hypotheses 1b and 1c is 4.8 lbs. We will have power of 0.94 for the one-sided test of hypothesis 1b (non-financial rewards are not inferior to financial rewards). The power for hypothesis 1c (regain is lower in the non-financial compared to financial reward arm) depends on expectations of regain. We extrapolated weight regain from the trials in Table 1 in two ways: a) by assuming the weekly weight regain between the end of rewards and the last measurement continued; and b) by using data from a systematic review that found that in randomized trials of lifestyle changes for weight loss with a one year follow-up, the mean weight loss at one year was about half the weight loss achieved at 6 months. (See 2.0 Introduction for details.) We estimate that the weight regain by 12 months in the financial reward arms would be around 7.2 lbs. Thus, in order to have 80% power to reject hypothesis 1c, regain in the non-financial reward arm would need to be at most 2.4 lbs. (i.e.,  $7.2-4.8=2.4$  lbs.). The power for subgroup analyses will be limited. Simulations suggest our study sample would need to increase four fold to detect an interaction between female and treatment arm with the same power as the main analysis. We will interpret the subgroup results as exploratory, although we note that the proposed study will enroll 5 times as many female Veterans (n=70) as were enrolled in the JAMA (2008) (n=3) and JGIM (2011) (n=11) trials, combined, and more than the total enrollment of either of those trials.

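### The hypothesis 1b rule sets no confidence bound against the 2.5 kg margin, and its closing sentence reverses the burden of proof, contrary to the one-sided test behind the stated 0.94 power

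*Combined protocol and SAP*

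**What the plan says.** All the relevant text for the test is in section 5.6.a (Data Analysis) of the combined protocol and SAP.

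- **The rule.** Hypothesis 1b is called a non-inferiority test. The paragraph says "We will reject the hypothesis that non-financial rewards are inferior to financial rewards if" two conditions hold: β2 (non-financial versus usual care) is significantly above zero, and β3 − β2 (financial minus non-financial, as mean weight loss) is less than 2.5 kg. Significance is attached to the first condition only.
- **The margin.** It is justified on the ground that "2.5 kg is half the 5 kg weight loss assumed to be clinically significant".
- **The closing sentence.** Values of the difference "that are statistically significantly larger than 2.5 kg are evidence against the hypothesis that non-financial rewards are not inferior to financial rewards".
- **The level.** "We used a two-sided alpha of 0.025 to account for the multiple comparisons between treatment groups (including for hypotheses 1b and 1c".
- **The power.** With 100 per reward arm, "the minimum detectable difference for hypotheses 1b and 1c is 4.8 lbs". The next sentence states: "We will have power of 0.94 for the one-sided test of hypothesis 1b". No one-sided level is given.
- **The variability.** "We assumed a standard deviation of 11.0 lbs. for weight loss".

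Section 3.0 (Objectives) sets the rank of this outcome: "Secondary outcomes include weight loss at 16 weeks and 12 months". Hypothesis 1b is a week-16 comparison.

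**The concern.** A non-inferiority claim needs the data to exclude a deficit as large as the margin, so the confidence limit, not the estimate, must fall inside it. The first sentence of the rule names the right null (inferiority), but the margin condition is then written on the difference itself. The closing sentence is the only place where significance meets the margin, and there non-inferiority plays the part of the null: it stands unless the data significantly contradict it.

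Two analysts could therefore disagree on the same data. Take an observed deficit of 4 lb with β2 significant. The written rule passes it, since 4 < 5.5. A one-sided 0.025 test fails it, because the upper limit is 4 + 1.960 × 1.556 = 7.05 lb. The claim at stake is that the non-financial reward works about as well as cash while rewards are being paid, which is one of the trial's three named hypotheses.

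**Working it through.** **Inputs.** The SD is 11 lb, the arms are 80 (usual care), 100 and 100, and the margin is 2.5 kg, or 5.5 lb (half of the plan's 11 lb). All are from section 5.6.a. The power check assumes no true difference between the reward arms, which the plan does not state. Normal approximations are used throughout.

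**Standard errors.**
- SE(β3 − β2) = 11 × √(2/100) = 1.556 lb
- SE(β2) = 11 × √(1/80 + 1/100) = 1.650 lb
- Covariance of the two estimates, through the shared non-financial arm = −121/100 = −1.21

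**1. The plan's own 0.94.** Power at no true difference is Φ(5.5/1.556 − z):

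| Margin condition | z | Power |
|---|---|---|
| Bound, one-sided 0.025 | 1.960 | 0.942 |
| Bound, one-sided 0.0125 | 2.241 | 0.902 |
| No bound (estimate below 5.5 lb) | 0 | 0.9998 |

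The 0.94 is reproduced by a bounded test at one-sided 0.025 with the stated 100 per arm. It is not the power of the rule as written.

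**2. The level.** The 4.8 lb detectable difference is (2.241 + 0.842) × 1.556 = 4.80 lb, which is two-sided 0.025. At two-sided 0.05 it would be (1.960 + 0.842) × 1.556 = 4.36 lb. So the 4.8 lb and the 0.94, in adjacent sentences about the same hypothesis, rest on different levels: one-sided 0.0125 and one-sided 0.025.

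**3. The largest observed deficit that passes.**
- As written: just under 5.5 lb
- One-sided 0.025: 5.5 − 1.960 × 1.556 = 2.45 lb
- One-sided 0.0125: 5.5 − 2.241 × 1.556 = 2.01 lb

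**4. False non-inferiority under the written rule.** Set the true deficit at the margin, so that β2 = β3 − 5.5, and test β2 at two-sided 0.025. The bivariate normal probability that the β2 estimate exceeds 2.241 × 1.650 = 3.70 lb and the difference estimate is below 5.5 lb is:

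| True β3, lb | Source | True β2, lb | Probability |
|---|---|---|---|
| 5.1 | Detectable difference, section 5.6.a | −0.4 | 0.006 |
| 6.5 | Table 1, proposed study: 8.1 − 1.6 | 1.0 | 0.044 |
| 8.4 | Section 5.6.a: 10 − 1.6 | 2.9 | 0.226 |
| 11.1 | Table 1, largest effect: 14.0 − 2.9 | 5.6 | 0.476 |

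As β2 grows, its condition is always met and the probability approaches 0.50. Testing β2 at two-sided 0.05 gives 0.073, 0.286 and 0.488 for the last three rows. With a confidence bound, the probability cannot exceed the chosen level, 0.025 or 0.0125, in any row.

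**5. The closing sentence used as a decision rule.** If non-inferiority were denied only when the deficit is significantly above the margin (one-sided 0.025), an observed deficit up to 5.5 + 1.960 × 1.556 = 8.55 lb would pass. The margin condition would then be met with probability 0.975 when the true deficit equals the margin.

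**The case against.** The best defence is that the paragraph, read with the power statement, describes an incompletely worded one-sided test. It names inferiority as the hypothesis to reject. The margin condition is written in the model's parameters and could be read as the alternative hypothesis. The closing sentence does not say that only significant excesses count, and a difference significantly above the margin is evidence against non-inferiority under any valid test. This is fair as an account of what was probably intended. It does not rescue the text: significance is written into one condition and left out of the other, nothing elsewhere supplies a bound, and the parallel closing sentence for hypothesis 1a describes evidence against the null.

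The source of the 0.94 can also be questioned. One-sided 0.05 with 80 completers per arm gives 0.935, which rounds to the same figure. But the plan says 100 per arm, and a level of 0.05 would lie further from its stated alpha.

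The size depends on the scenario, and that point stands. The β2 condition filters results: with a financial effect of only 5.1 lb the error is 0.006, below either level. The 0.48 comes from a deposit-contract arm of 19 people, a different reward design. The 8.4 lb case (0.23) is the fairest single illustration, since it uses the plan's own average across earlier trials.

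**Conclusion.** The concern holds. As written, the rule can declare non-inferiority far more often than any level in the plan allows: 0.23 at the average effect the plan cites, 0.04 at the effect in its own Table 1 column, and at most 0.50. These figures assume an SD of 11 lb, full enrolment at 80/100/100 and a true deficit equal to the margin. The missing bound does not depend on how the closing sentence is read. That sentence makes the error worse only if it is used to decide.

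The conflict over the level is smaller but real: power is 0.94 at one-sided 0.025 and 0.90 at the one-sided 0.0125 that the alpha statement implies. The outcome is secondary, so this should be fixed, but it does not threaten the primary result.

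**What to change.** In section 5.6.a:

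1. Declare non-inferiority at week 16 only if β2 is significantly above zero **and** the upper confidence limit of β3 − β2 is below 2.5 kg.
2. State that the outcome is coded as weight loss for this test. Equation (1) defines it as change in weight, for which a positive β2 would mean less loss.
3. Replace the closing sentence with: if the upper limit is 2.5 kg or more, non-inferiority is not shown.
4. State one one-sided level and make the alpha statement, the detectable difference and the power agree with it. One-sided 0.025 keeps the 0.94 but needs the alpha statement amended for 1b, and the 4.8 lb restated as 4.36 lb for that hypothesis. One-sided 0.0125 keeps the alpha statement and the 4.8 lb, and the 0.94 becomes 0.90.

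The cost is wording and one decision, with no change to sample size, visits or data. The claim becomes harder to meet:

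| One-sided level | Margin test, 100 per arm | Margin test, 80 completers per arm | Both conditions, full enrolment |
|---|---|---|---|
| 0.025 | 0.94 | 0.89 | 0.91 |
| 0.0125 | 0.90 | 0.82 | 0.87 |

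The 80 completers apply the plan's 20% loss to follow-up (SE = 11 × √(2/80) = 1.739 lb). The last column assumes no true difference between the reward arms and β2 = 6.5 lb, with β2 tested at two-sided 0.025.
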